9.4.3.2 Severity

For laboratory AEs, the severity should be indicated according to Appendix D, which is based on the National Cancer Institute Common Terminology Criteria for Adverse Events (CTCAE) guidelines, Version 4.03.

For AEs not listed in Appendix D, the event's severity is characterized by 1 of the following:

- **Mild:** The event is easily tolerated by the patient and does not affect the patient's usual daily activities
- Moderate: The event causes the patient more discomfort and interrupts the patient's usual daily activities
- **Severe:** The event is incapacitating and causes considerable interference with the patient's usual daily activities

9.4.3.3 Action Taken with Study Drug

Action taken with RO7234292 due to the event is characterized by 1 of the following:

- None: No changes were made to RO7234292 administration and dose
- **Permanently Discontinued:** RO7234292 was discontinued and not restarted
- Temporarily Interrupted, Restarted Same Dose: Dosing was temporarily interrupted
 or delayed due to the AE and restarted at the same dose

9.4.3.4 Treatment Given for Adverse Event

Any treatment (e.g., medications or procedures) given for the AE should be recorded on the Adverse Event Case Report Form. Treatment should also be recorded on the concomitant treatment or ancillary procedures eCRF, as appropriate.

9.4.3.5 Outcome of the Adverse Event

If the event is a non-serious AE, then the event's outcome is characterized by 1 of the following:

- AE Persists: Patient terminates from the trial and the AE continues
- **Recovered:** Patient recovered completely from the AE
- Became Serious: The event became serious (the date that the event became serious should be recorded as the Resolution Date of that AE and the Onset Date of the corresponding SAE)
- Change in Severity (if applicable): AE severity changed

If the event is an SAE, then the event's outcome is characterized by 1 of the following:

- Ongoing: SAE continuing
- Persists (as non-serious AE): Patient has not fully recovered but the event no longer
 meets serious criteria and should be captured as an AE on the non-serious AE eCRF (the
 SAE resolution date should be entered as the date of onset of that AE)
- Recovered: Patient recovered completely from the SAE (the date of recovery should be entered as the SAE resolution date)
- Fatal: Patient died (the date of death should be entered as the SAE resolution date)

9.5 Procedures for Handling Special Situations

9.5.1 Abnormalities of Laboratory Tests

Clinically-significant abnormal laboratory test results may, in the opinion of the Investigator, constitute or be associated with an AE. Examples of these include abnormal laboratory results that are associated with symptoms, or require treatment, e.g., bleeding due to thrombocytopenia, tetany due to hypocalcemia, or cardiac arrhythmias due to hyperkalemia. Whenever possible, the underlying diagnosis should be listed in preference to abnormal laboratory values as AEs. Clinically-significant abnormalities will be monitored by the Investigator until the parameter returns to its baseline value or until agreement is reached between the Investigator and Sponsor Medical Monitor. Laboratory abnormalities deemed not clinically-significant (NCS) by the Investigator should not be reported as AEs. Similarly, laboratory abnormalities reported as AEs by the Investigator should not be deemed NCS on the laboratory sheet.

The Investigator is responsible for reviewing and signing all laboratory reports. The signed clinical laboratory reports will serve as source documents.

9.5.2 Prescheduled or Elective Procedures or Routinely Scheduled Treatments

A prescheduled or elective procedure or a routinely scheduled treatment will not be considered an SAE, even if the patient is hospitalized; the Study Center must document all of the following:

- The prescheduled or elective procedure or routinely scheduled treatment was scheduled (or was on a waiting list to be scheduled) prior to obtaining the patient's consent to participate in the Study
- The condition that required the prescheduled or elective procedure or routinely scheduled treatment was present before and did not worsen or progress in the opinion of the Investigator between the patient's consent to participate in the Study and the timing of the procedure or treatment
- The prescheduled or elective procedure or routinely scheduled treatment is the sole reason for the intervention or hospital admission

9.5.3 Dosing Errors

RO7234292 dosing errors should be documented as Protocol Deviations. A brief description should be provided in the deviation, including whether the patient was symptomatic (list symptoms) or asymptomatic, and the event accidental or intentional.

Dosing details should be captured on the Dosing Case Report Form. If the patient takes a dose of RO7234292 that exceeds protocol specifications and the patient is symptomatic, then the symptom(s) should be documented as an AE and be reported per Section 9.4.

Should an overdose occur, the Investigator or designee should refer to the Guidance to Investigator's section of the Investigator's Brochure and contact the Sponsor or designee within 24 hours.

9.5.4 Contraception and Pregnancy

Patients must continue to use appropriate contraception with their partners, or refrain from sexual activity, as described in Section 6.3.1.

If a patient becomes pregnant or a pregnancy is suspected, or if a male patient makes or believes that he has made someone pregnant during the Study, then the Study Center staff must be informed immediately. An Initial Pregnancy Form should be submitted to the Sponsor or designee within 24 hours of first learning of the occurrence of pregnancy. Follow-up information including delivery or termination is reported on Follow-up Pregnancy Forms and reported within 24 hours.

Payment for all aspects of obstetrical care, child or related care will be the patient's responsibility.

Female patients: If a suspected pregnancy occurs while on the Study (including follow-up), a pregnancy test will be performed. The patient with a confirmed pregnancy will be immediately withdrawn from treatment with RO7234292. However, the patient will be encouraged to complete the post-treatment follow-up portion of the study to the extent that study procedures do not interfere with the pregnancy. Regardless of continued study participation, the study physician will assist the patient in getting obstetrical care and the progress of the pregnancy will be followed until the outcome of the pregnancy is known (i.e., delivery, elective termination, or spontaneous abortion). If the pregnancy results in the birth of a child, the Study Center and Sponsor may require access to the mother and infant's medical records for an additional 8 weeks after birth.

Amendment 4 (Version 5)

Male patients: The progress of the pregnancy of a male patient's partner should be followed until the outcome of the pregnancy is known (i.e., delivery, elective termination, or spontaneous abortion). If the pregnancy results in the birth of a child, additional follow-up information may be requested for the mother and infant. Follow-up will be performed to the extent permitted by the applicable regulations and privacy considerations.

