 RO7234292 administration frequency according to cohort assignment (see cohort dosing regimens on next page)

POST-TREATMENT PERIOD / END-OF-STUDY / EARLY TERMINATION

Weeks 63-74

 One (1) post-treatment visit for final study assessments in patients who will not enter the open-label extension study (BN40955)

COHORT DOSING REGIMENS

STUDY GLOSSARY	
Abbreviation	Definition
2'-MOE	2'-O-(2-methoxyethyl)
AE	Adverse event
ALT	Alanine aminotransferase (SGPT)
AP	Anterior-posterior
aPTT	Activated partial thromboplastin time
AST	Aspartate aminotransferase (SGOT)
βhCG	Beta-subunit of human chorionic gonadotropin (pregnancy test)
Bimonthly	Every other month
ВР	Blood pressure
BUN	Blood urea nitrogen
cl	clinic
CRF	Case report form
CSF	Cerebrospinal fluid
C-SSRS	Columbia suicide severity rating scale
CTCAE	Common Terminology Criteria for Adverse Events
ECG	Electrocardiogram
eCRF	Electronic Case Report Form
EEG	Electroencephalogram
FSE	Fast spin echo
GCP	Good Clinical Practice
HD	Huntington's disease
HDID	Huntington's disease identification number
HDWF	Huntington's disease work function

Htt Huntingtin / Htt protein

HR Heart rate

ICH International Conference on Harmonization

IEC Independent Ethics Committee

IL-1β Interleukin-1 beta

IMP investigational medicinal product

INR International normalized ratio
IRB Institutional Review Board

IT Intrathecal(ly)

MAD Multiple-ascending dose

MCH Mean corpuscular hemoglobin

MCHC Mean corpuscular hemoglobin concentration

MCV Mean corpuscular volume

MedDRA Medical Dictionary for Regulatory Activities

MRI Magnetic resonance imaging

mRNA Messenger ribonucleic acid

NCS Not clinically-significant

OLE Open-label extension

on Study The patient is 'on Study' from signing of the informed consent until his/her last

study visit

OTS One touch stockings

pH Measure of the acidity or basicity of a solution

ph phone

PK Pharmacokinetic(s)

PBA-s Problems behavior assessment for Huntington's disease – short form

PT Prothrombin time qEEG Quantitative EEG

RO7234292 Antisense inhibitor of HTT, previously known as ISIS 443139

RNase H1 Ribonuclease H1 (a non-specific endonuclease and catalyzes the cleavage of

RNA via a hydrolytic mechanism)

SAE Serious adverse event

siRNA Small interfering ribonucleic acid

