3.4.3 Post-Treatment Period

After completing study treatment in Study BN40697, the patient will be eligible to enroll in another OLE study (BN40955) with active RO7234292 compound, provided the data from the ongoing RO7234292 program support continued development, the patient meets the inclusion and exclusion criteria for the OLE, and the OLE meets approval by the relevant competent authorities, IRBs, and ECs.

Patients who will not enter the OLE study will return to the Study Center for one follow-up visit 14 weeks after the last dose of RO7234292. The final study visit will be Study Day 428/Week 62 for patients who enter OLE Study BN40955 and Study Day 519/Week 74 for those patients who do not.

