6.3 Restriction on the Lifestyle of Patients

6.3.1 Contraception Requirements

All male patients and women patients of childbearing potential must refrain from sperm/egg donation and practice effective contraception from the time of signing the informed consent form until at least 5 months after the last dose of RO7234292.

Male patients must also encourage their female partner to use effective contraception from the time of signing the informed consent through the end of the study.

For the purposes of this study, women of childbearing potential are defined as any female who has experienced menarche and does not meet 1 of the following conditions:

- Postmenopausal: 12 months of spontaneous amenorrhea without an alternative medical cause and FSH levels in the postmenopausal range for the laboratory involved
- 6 weeks after surgical bilateral tubal occlusion, hysterectomy, bilateral salpingectomy or bilateral oophorectomy with or without hysterectomy
- Post hysterectomy

For the purposes of the study, effective contraception is defined as follows:

For male patients:

- Effective male contraception includes a vasectomy with negative semen analysis at follow-up, or the use of condoms together with spermicidal foam/gel/film/ cream/suppository
- Male patients with partners that are pregnant must use condoms as contraception to ensure that the fetus is not exposed to the *RO7234292*

For female patients:

Surgical sterilization (e.g., bilateral tubal occlusion, hysterectomy, bilateral salpingectomy, bilateral oophorectomy) or using 2 methods from signing ICF until at least 5 months after the last dose of RO7234292. The 2 methods should include at least 1, highly-effective barrier method (e.g., intrauterine device or any of the following in combination with spermicidal foam/gel/film/cream/suppository: male condom*, female condom*, diaphragm, sponge, cervical cap) and at least 1 other method (e.g., oral, injected or implanted hormonal methods).

For female partners of male patients:

Using any of the following acceptable methods of contraception: surgical sterilization
 (e.g., bilateral tubal occlusion, hysterectomy, bilateral salpingectomy, bilateral
 oophorectomy); oral, injected or implanted hormonal contraception; intrauterine
 contraception/device; or any 2 barrier methods (a combination of male or female
 condom* with diaphragm, sponge or cervical cap) together with spermicidal
 foam/gel/film/cream/suppository

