9.3.3 Serious Adverse Event (SAE)

A serious adverse event is any AE that in the view of either the Investigator or Sponsor, meets any of the following criteria:

- Results in death
- Is life threatening: that is, poses an immediate risk of death at the time of the event

 An AE or suspected adverse reaction is considered "life-threatening" if, in the view of
 either the Investigator or Sponsor, its occurrence places the patient at immediate risk of
 death. It does not include an AE or suspected adverse reaction that, had it occurred in a
 more severe form, might have caused death
- Requires inpatient hospitalization or prolongation of existing hospitalization
 Hospitalization is defined as an admission of greater than 24 hours to a medical facility and does not always qualify as an AE
- Results in a persistent or significant incapacity or substantial disruption of the ability to conduct normal life functions
- Results in a congenital anomaly or birth defect in the offspring of the patient (whether the patient is male or female)
- Important medical events that may not result in death, are not life-threatening, or do
 not require hospitalization may also be considered serious when, based upon
 appropriate medical judgment, they may jeopardize the patient and may require
 medical or surgical intervention to prevent 1 of the outcomes listed in this definition.
 Examples of such medical events include allergic bronchospasm requiring intensive
 treatment in an emergency room or at home, blood dyscrasias or convulsions that do

not result in inpatient hospitalization, or the development of drug dependency or drug abuse

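### For patients not entering BN40955, scheduled contact ends about 54 days before the 5-month contraception duty, and partner-pregnancy reporting in Section 9.5.4 is not tied to that duty

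*Combined protocol and SAP*

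**What the plan says.** Section 6.3.1 requires male patients and women of childbearing potential to use contraception "until at least 5 months after the last dose of RO7234292". The sentence asking male patients to encourage their partners' contraception has a different end point: "from the time of signing the informed consent through the end of the study".

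Section 3.4.3 gives patients who do not enter BN40955 "one follow-up visit 14 weeks after the last dose", at Study Day 519, and makes it their final study visit. In the visible part of Appendix A, that visit holds the last pregnancy test and the last contact of any kind.

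Section 9.5.4 sets out the reporting duty. For patients themselves it says "If a patient becomes pregnant or a pregnancy is suspected", with no evident time limit. For partners it says "or if a male patient makes or believes that he has made someone pregnant during the Study". A pregnancy test in a female patient is called for under the condition "If a suspected pregnancy occurs while on the Study (including follow-up"). The glossary states "The patient is 'on Study' from signing of the informed consent until his/her last" study visit, while Section 3.5 defines End-of-Study at trial level, as the last visit of the last patient.

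Section 9.3.3 counts as serious any event that "Results in a congenital anomaly or birth defect in the offspring of the patient (whether the patient is male or female"). Section 9.4.1 stops SAE collection at Day 519 or at enrolment in BN40955.

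**The concern.** The protocol uses two clocks for one risk. By requiring contraception for 5 months, it treats conception as an exposure concern for that long. The schedule, and on one reading the partner-reporting duty, stop at 14 weeks.

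Take a partner pregnancy conceived 17 weeks after the last dose. It falls inside the period in which the protocol wants conception avoided. With the final visit on its nominal date, no scheduled contact remains at which it would come to light, and on the patient-level reading the site has no instruction to report it. A fetal exposure of this kind is individually informative and hard to recover later.

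**Working it through.** **Inputs.** Doses every 28 days (Monthly), or two doses 28 days apart and then every 56 days (Bimonthly); final visit Day 519 with a window of ±21 days; maintenance dosing visits ±5 days (all Appendix A). Appendix A calculates windows from Study Day 1, so the dose and the final visit can move independently. Contraception runs to at least 5 months after the last dose (Section 6.3.1).

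**Reproducing the plan's own figure.**
- Monthly last dose: 1 + 15 × 28 = Day 421.
- Bimonthly last dose: 29 + 7 × 56 = Day 421.
- Last dose to final visit: 519 − 421 = 98 days = 14 weeks, as Section 3.4.3 states.

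**Length of 5 months.** 5 × 30.44 = 152 days. By calendar, the range is 150 days (February to June, non-leap year: 28 + 31 + 30 + 31 + 30) to 153 days (March to July: 31 + 30 + 31 + 30 + 31).

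**Gap between the final visit and the end of the contraception duty.**

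| Case | Days from last dose to visit | Gap in days |
|---|---|---|
| Nominal, 152-day period | 98 | 152 − 98 = 54 |
| Nominal, calendar range | 98 | 150 − 98 = 52 to 153 − 98 = 55 |
| Visit ±21 (Day 498 to 540) | 77 to 119 | 150 − 119 = 31 to 153 − 77 = 76 |
| Visit ±21 and dose ±5 (Day 416 to 426) | 498 − 426 = 72 to 540 − 416 = 124 | 150 − 124 = 26 to 153 − 72 = 81 |

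Even if a month is taken as 28 days, the nominal gap is 140 − 98 = 42 days. It is positive in every case. The nominal end of the duty is 421 + 152 = Day 573.

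**The 17-week example.** 17 × 7 = 119 days after the dose: 119 − 98 = 21 days after the nominal visit, and 152 − 119 = 33 days before the duty ends.

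**Two readings of the partner clause.**
- Patient level (glossary): reporting stops at the patient's last visit, so the reporting gap equals the contact gap in the table.
- Trial level (Section 3.5): the window runs to the last patient's last visit. It may reach 5 months for patients who finish early, but its length depends on when others finish. The last patient, if not rolling over, has the same gap as before.

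On either reading, no contact is scheduled after Day 519.

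**SAE classification.** The documents give no time from conception to birth; assume 266 days (range 245 to 280). Conception on Day 421 gives birth on about Day 687 (666 to 701), which is 168 days (147 to 182) after Day 519. Conceptions before about Day 519 − 266 = 253 (range 239 to 274) would deliver before the stop, so the issue concerns later conceptions.

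**The case against.** The strongest objection is that the reporting gap depends on one reading. The glossary defines being on study for a patient; the partner clause uses a slightly different phrase, and Section 3.5 offers a trial-level end. That is fair. A reader might infer that the protocol plainly ends partner reporting at Day 519; it does not say so. What stands is that neither reading ties the window to 5 months.

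Second, a reader might infer that a female patient's own pregnancy after Day 519 need not be reported. The text does not support this, because the time limit arguably does not attach to that clause. For female patients the weakness is the lack of a later scheduled contact, together with a testing instruction confined to time on study and follow-up.

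Third, a reader might infer that birth defects after Day 519 are lost. Section 9.5.4 already follows reported pregnancies to outcome, with follow-up forms due within 24 hours and possible access to infant information. Section 9.3.3 also lets the Sponsor judge seriousness. What remains is whether a late birth defect is classified and handled as an SAE, which sites could decide differently.

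Fourth, the consent pages, the Safety Management Plan and the Study Reference Manual were not available and may carry further instructions. Section 9.5.4 also tells patients to continue contraception and to inform the site at once. Even so, the protocol's own instruction to sites should give a clear end point.

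Finally, nothing in the protocol requires scheduled contact to last as long as a contraception precaution. That is why the call proposed below is optional.

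**Conclusion.** The point holds as a small, cheap improvement. For patients who do not enter BN40955, the last scheduled contact and pregnancy test falls about 54 days before the contraception duty ends (52 to 55 nominal; 31 to 76 with the visit window; 26 to 81 with both windows). Partner-pregnancy reporting stops equally early if the clause is read at patient level. Read at trial level, its end is not tied to 5 months.

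The figures assume a last dose at about Day 421. Early terminators who attend the 14-week visit have about the same gap. The number affected is unknown: it is limited to non-roll-over patients who can conceive or whose partner can, out of at most 46, and sterile, post-menopausal and abstinent patients are admitted. Few events are expected.

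Roll-over patients are outside this finding. The partner-encouragement wording in Section 6.3.1 is only a consistency matter, since the male patient's own duty already runs to 5 months. A reader might also infer an effect on the trial's results; sample size, error rate and the Section 10.6 analyses are all untouched.

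**What to change.** 1. In Section 9.5.4, add: *For patients who do not enter Study BN40955, a pregnancy in a patient or in the partner of a male patient is reportable if conception occurs up to 5 months after the last dose of RO7234292 in this study. A congenital anomaly from any reported pregnancy is reported as an SAE regardless of the collection stop in Section 9.4.1.* Limiting the first sentence to non-roll-over patients and to the last dose in this study avoids duplicating reports in BN40955.
2. In the partner-encouragement sentence of Section 6.3.1, replace the end-of-study limit with "until at least 5 months after the last dose of RO7234292".
3. At the Day 519 visit, remind patients that the contraception and reporting duties continue.
4. Optional: one telephone call at or after about Day 573 for these patients, unless consent has been withdrawn. A call on Day 573 itself may miss very recent conceptions. Appendix A treats telephone contacts as visits, so the amendment should say whether the call counts towards End-of-Study.

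**Cost.** A minor amendment and consent wording, with the authority and ethics handling in Section 12.1. Pregnancy capture closes about 54 days later, and any additional pregnancy reported would be followed to outcome under the existing rule. If the call is adopted, it adds one contact per non-roll-over patient.

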10. STATISTICAL CONSIDERATIONS

10.1 Study Endpoints, Subsets, and Covariates

There is no single primary endpoint for this study. Important endpoints that will be evaluated are identified in the following sections.

10.1.1 Safety and Tolerability Endpoints

- Columbia Suicide Severity Rating Scale (C-SSRS)
- Physical examination and standard neurological assessment (including fundi)
- Pregnancy testing
- Vital signs (heart rate [HR], BP, orthostatic changes, weight)
- ECG
- AEs and concomitant medications
- CSF safety labs (cell counts, protein, glucose)
- Plasma laboratory tests (clinical chemistry, hematology)
- Urinalysis
- Safety neuroimaging assessments

